### **2.18 Early experience with the regimen.**

The first five patients were treated with 600mg of Hydroxychloroquine with one patient deemed a complete response. Out of the 13 patients treated with combination HCQ/IL-2 therapy using 1200 mg of Hydroxychloroquine, two patients experienced pronounced hypotension and tachycardia. Furthermore, one patient died from pulmonary emboli, not attributed to therapy. The cardiac events are consistent with IL-2 toxicities, but were observed somewhat earlier in the course of treatment. For that reason we are accruing another 21 patients to assess response in addition to the first five patients at the lower 600mg/d dose.

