## 7.2 Serum and PBMC

- a. All serum and plasma samples will be aliquoted and stored at -70 to -80°C at the UPCI. Specimens will be sent overnight to the IMCPL/UPCI (see Appendix D):
- b. Blood samples will be used for:
  - 1) Western Blots and EM for measures of autophagy (LC3, p62, Caveolin 1, HMGB1, sRAGE)-Research Laboratory (DAMP Laboratory)
  - 2) Serum angiogenic cytokine measurements including VEGF, ANG1, and ANG2; Fibronectin; Osteopontin (IMCPL)
  - 3) Immune Function: TCR zeta chain, serum arginase/arginine levels (IMCPL)
  - 4) Phenotype: KIRS, T cells, Treg, MDSC, NK cells, Measures of CD11b+IL4Rα+ myeloid derived suppressor cells, CD56bright and CD56dull NKp46+ NK cells, and LineageHLA-DR+ myeloid DCs, and CD123+Lineage plasmacytoid DCs will be assessed. Measures of cell surface RAGE and cytosolic RAGE on permeabilized cells will also be carried out. (IMCPL)
  - 5) miRNA-Research Laboratory (DAMP Laboratory)
  - 6) Bank DNA and/or RNA (i.e. RNA PAX tubes) for germline SNP, gene expression analysis etc.) See 7.5.

Autophagy assays will be run on all specimens

**7.3 Correlate the level of autophagy in resected renal adenocarcinomas (where available) with measures of clinical outcome and response.** We hypothesize that levels of autophagy in biopsies from patients on treatment will directly correlate with response to therapy. Fixed specimens in 10% formalin at room temperature, and the size and gross appearance of the tumors will be recorded. Select serial sections of the tumor specimens will be assessed for

clinicopathologic correlates, HMGB1, RAGE, LC3, Caveolin 1, and p62 staining as described below. The immunohistochemical staining results will then be analyzed statistically to examine the relationship between clinicopathological factors in the tumor, disease-free survival and overall survival.

*Clinicopathological Correlates:* 1) tumor size ( $\geq 3$  vs  $< 3$  cm); 2) predominant differentiation of the tumor (well, moderately, or poorly differentiated); 3) lowest degree of tumor differentiation 4) angiolymphatic invasion 5) neural invasion; 6) margin status; 7) International Union Against Cancer (UICC) pathological T and N stage.

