## 13.0 STATISTICAL ANALYSIS AND STUDY SIZE

### 13.1 Objectives and Design

The primary objective of this Phase II trial is to estimate the proportions of patients with metastatic RCC treated with high-dose IL-2 combined with hydroxychloroquine experiencing complete response, or any response. The secondary objectives are to compare response, time to progression and survival to historical data to determine the toxicity of the treatment regimen, to evaluate PD, and to examine correlative science endpoints. Disease endpoints are defined in Section 10.

The accrual goal is 39 participants. All study participants will receive the same high-dose IL-2 treatment, which is considered standard of care. The initial dose of HCQ will be 600 mg/day for all patients. If no limitations on additional dosing (treatment-limiting toxicities [TLTs], as defined in Section 9.2), dosing will continue at 600mg/d, otherwise, HCQ will de-escalate to 400 mg/d. Toxicity and response will be monitored after every three patients (Section 13.4), and will be stopped if the probability that treatment with IL-2+HCQ is excessively toxic or ineffective. The study may be opened more broadly to additional Cytokine Working Group sites whenever sufficient evidence has accrued that treatment with IL-2+HCQ is no more toxic or less effective than treatment with IL-2 alone.

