This prognostic classification will be added to the baseline models described in Sections 13.2.1 to 13.2.3 to determine if any of the factors would significantly change the prognostic evaluation, and to the dynamic and post-treatment factors to potentially increase the statistical power.

**13.2.5** *Correlate baseline laboratory parameters (miRNAs pre- and post-IL-2; KIR genotyping; NK enumeration in the peripheral blood; DC function, TCR- $\zeta$  chain expression, arginase or arginine levels, proposed pathological/molecular prognosis classification described in Section 2.6) with toxicity, response, and survival.* Stepwise proportional hazards or logistic regression will be used to add variables to the models resulting from the analyses in Section 13.2.4.

**13.2.6** *Assess if changes in biomarkers measured in PBMC (Section 7.4) are associated with clinical response, overall survival or progression-free survival.* Stepwise proportional hazards or logistic regression will be used to determine if changes of any of the markers in Section 7.4 are related to patient outcomes, after adjusting for the prognostic criteria in 13.2.4.

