### **13.3 Monitoring for Toxicity and Response**

**13.3.1** 21 additional patients will be enrolled at IL-2+HCQ 600 mg/day on this revised protocol. If one or more TLTs are observed, treatment will be de-escalated to IL-2+HCQ 400 mg/day.

**13.3.2** The number of overall partial and complete responses (**Table 8**) will be compared to the stopping rule described in Table 10 by the UPCI Multi-Center DSMC after every three patients become evaluable for response. For each number of evaluable patients in the left-hand columns, if the number of complete responses is less than or equal to the number in the right-hand column, the trial will be halted for lack of efficacy. The trial is derived from a Bayesian beta-binomial model with the prior determined by the number of complete responses observed in the high-dose arm of the randomized trial described in Section 2.3 (8/95). The values correspond to P (partial and complete response rate < 0.10) > 0.8.

# Patients	#Responses
18	0
21	1
24	1
27	1
30	2
33	2
36	2

*Table 8.* Monitoring rule for complete response. For the given number of patients in Column 1, if the number of partial or complete responses is less than or equal to the number in Column 2, the trial is halted for lack of efficacy.

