### 13.4 Justification of Design

The primary objective of this study is to estimate the clinical response rate of patients with metastatic RCC treated with IL-2 combined with hydroxychloroquine at 600mg/d. Assuming no TLTs occur and the trial is not closed early for toxicity or inadequate response (Section 13.3.2), there will be 39 patients available for this objective. A 95% exact binomial confidence interval on 5 responses out of 39 patients (expected if the addition of HCQ to IL-2 doubles the historic proportions of CR ~ 8%) would have width equal to 0.27 (0.07,0.34). For the secondary endpoints of OS and PFS, if patients are recruited over 15 months, observed for 15 additional months, and the true median survival is 16 months, then the expected width of the 95% confidence interval for median survival is 12.8 months.

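### Sections 13.2.5 and 13.2.6 select markers stepwise with few events and no stated threshold or error control; single-marker models with false-discovery control would be better

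*Combined protocol and SAP*

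**What the plan says.** The analysis plan is Section 13 of the combined protocol and SAP. Section 13.2.4 adds the prognostic classification to the outcome models. Section 13.2.5 then relates laboratory parameters to survival, to response and to toxicity. Its stated method is: "Stepwise proportional hazards or logistic regression will be used to add variables to the models resulting from the analyses in Section 13.2.4". Section 13.2.6 relates changes in PBMC markers to clinical response, overall survival (OS) and progression-free survival (PFS), adjusted for the same prognostic criteria. Its method sentence begins: "Stepwise proportional hazards or logistic regression will be used to determine if changes of any of the markers"; the markers meant are those listed under Section 7.4.

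Neither section states a threshold to enter or stay, a limit on the number of variables, a multiplicity rule or a validation step. Section 13.2.2 says that its own historical comparisons are not powered. No such caveat is attached to 13.2.5 or 13.2.6.

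On size, Section 13.1 says "The accrual goal is 39 participants" and Section 13.3.1 says "21 additional patients will be enrolled at IL-2+HCQ 600 mg/day on this revised protocol". Section 2.18 adds "For that reason we are accruing another 21 patients to assess response in addition to the first five patients at the lower 600mg/d dose", and also reports "Out of the 13 patients treated with combination HCQ/IL-2 therapy using 1200 mg of Hydroxychloroquine". Section 13.4 works with 5 responses in 39, "expected if the addition of HCQ to IL-2 doubles the historic proportions of CR ~ 8" per cent.

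**The concern.** A stepwise search keeps whichever candidates look best in the data and then reports them as if they had been chosen in advance. With many candidates and few events, pure noise is often selected, and the reported p-values and intervals take no account of the search. The plan leaves open the setting that most determines how often this happens, namely the entry and stay rule.

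The stake is the correlative programme. Section 2.13 intends the miRNA profiles of responders and non-responders as a training set for predicting benefit from IL-2. The protocol also knows how fragile such findings can be. Section 2.6 reports a combined pathology and CAIX grouping with an odds ratio of 30 in 66 patients, 27 of them responders, and then says that the later prospective study could not establish these features as a predictor. That grouping was not derived by the stepwise method planned here, but it rested on far more responders than this trial expects.

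**Working it through.** **1. The plan's own figures.** No error rate is given for the biomarker analyses. Section 13.4 has two figures that fix the scale of events.

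- OS: median 16 months, 15 months' accrual, 15 months' further follow-up. With an exponential rate λ = ln 2/16 = 0.0433, the expected proportion dead is 1 − (e^(−15λ) − e^(−30λ))/(15λ) = 1 − (0.522 − 0.273)/0.650 = 0.616. That is 24.0 deaths in 39 and 16.0 in 26. The interval width for the median is 2 × 1.96 × 16/√24.0 = 12.8 months, which reproduces the plan.
- Complete response (CR): the exact 95% interval for 5 of 39 is (0.043, 0.274), width 0.231. The plan prints (0.07, 0.34), width 0.27, which does not reproduce. This is a separate matter; only the count of 5 is used here.

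**2. Events.** Section 2.18 gives 5 + 21 = 26 patients at 600 mg/d. The total of 39 equals 5 + 13 + 21, so it appears to count the 1200 mg patients. Sections 13.2.5 and 13.2.6 do not say which set they use, so both are shown.

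- CR at 8%: 26 × 0.08 = 2.1.
- CR at 16%: 26 × 0.16 = 4.2; 39 × 0.16 = 6.2.
- CR at the plan's 5/39 = 12.8%: 26 × 0.128 = 3.3.
- Any response at the comparison trial's 25% (Section 2.2): 26 × 0.25 = 6.5; 39 × 0.25 = 9.8.

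**3. Candidates.** Section 13.2.5 lists seven items, one of which is miRNAs, number not stated. With the three miRNAs named in Section 2.13, that makes 6 + 3 = 9. With the nine from the preliminary data in the same section, it makes 6 + 9 = 15. Section 7.4 names seven proteins for 13.2.6. Together that is 16 to 22. The 25-marker row below goes beyond these lists and is illustrative.

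**4. Chance of at least one false marker when none is real.** For m independent markers and entry level α it is 1 − (1 − α)^m. At α = 0.05, for example, 1 − 0.95^16 = 56%. It was also simulated for logistic models with 4 responders in 26 (1000 runs per setting, independent normal markers, score test to enter).

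| Markers | Formula, 0.05 | Simulated entry, 0.05 | Simulated, AIC | Kept under Wald stay rule, 0.05 |
|---|---|---|---|---|
| 7 | 30% | 31% | 74% | 11% |
| 9 | 37% | 36% | 81% | 13% |
| 16 | 56% | 58% | 96% | 23% |
| 25 | 72% | 73% | almost 100% | 32% |

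A further simulation gave 31%, 39%, 59% and 73% for entry at 0.05, with similar rates for 6 responders in 26, for 6 in 39, and for Cox models of OS.

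Sensitivity with 16 markers:

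- Markers correlated at 0.3 and 0.5: entry in 49% and 41%.
- 5 of 39: entered 58%, kept 42%.
- 7 of 26: entered 57%, kept 37%.

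The figures are for one outcome. For 9 markers and three outcomes, treating the outcomes as independent gives 1 − 0.63³ = 75%; related outcomes would give less.

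**5. The alternative on the same data.** One exact rank test per marker, with Benjamini-Hochberg at q = 10% and all markers null (4 of 26, 7 to 25 markers), gives any false marker in 6–11% of runs. Allowing for the spread between simulations, this is about 6–12%. The same tests at 0.05 without correction give 29–71%, so the gain comes from the error control and not from testing singly.

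Power for one true marker among 16 at q = 10%, with 4 of 26, is 9% at AUC 0.75, 33% at 0.85 and 81% at 0.95. For a binary marker carried by 13 of 26, even if all 4 responders carry it, the two-sided Fisher p is 2 × 715/14950 = 0.096.

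**The case against.** The strongest reply is that CR is only the sparsest reading. The outcomes in 13.2.5 and 13.2.6 include response in general, survival and, in one section each, toxicity or PFS, and Cox regression is named first. With about 16 deaths in 26, separation is not the issue it is for CR. That stands for separation. It does not rescue the method, because the false-entry rate depends mainly on the number of candidates and the threshold, and it is similar for the Cox models.

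A reader might infer that the plan will usually report a false marker. The documents do not support this. At entry 0.05 it takes about 14 independent markers to pass 50% (1 − 0.95^14 = 51%), or about 5 under an AIC-type rule (1 − 0.843^5 = 57%). It fails for the 7- or 9-marker list alone at 0.05, for 16 markers correlated at 0.3 to 0.5, and in every simulated setting with a 0.05 Wald stay rule. In the sparse CR models, part of that last protection comes from separation and inflated standard errors, which is not designed error control.

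A reader might also infer that most correlative findings would be artefacts. The calculation gives the chance of any false entry when every marker is null. It does not give the share of reported findings that are false. Nor are the intervals necessarily too narrow everywhere: separation makes them very wide.

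Finally, these are secondary, correlative analyses. That limits the consequence but does not justify the method.

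**Conclusion.** The concern holds in this form: stepwise selection is prescribed over an assumed 9 to 22 candidates, with few events and no stated threshold, error control or validation. With entry at 0.05, independent markers and no true association, a given search admits at least one null marker in about 31% of trials with 7 candidates, 36–39% with 9, 56–59% with 16 and 72–74% with 25. The range under other rules is wide: 74% with 7 markers under AIC, but 11–32% with a 0.05 Wald stay rule at 4 of 26. Searching over several outcomes raises it.

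The entry rule, the marker count and independence are assumptions, because the documents fix none of them. The figure of about 4 complete responders is derived from 26 × 16% and applies to CR only. A better method exists for the same data, so this is more than missing detail. It does not touch the primary estimate or the stopping rule.

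**What to change.** In Sections 13.2.5 and 13.2.6, replace stepwise selection as follows.

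- Fit one model per marker and outcome. Use exact, permutation or Firth-penalised inference for binary response, and Cox models for OS and PFS.
- Adjust for the prognostic group only where the number of events allows. Leave sparse CR models unadjusted: with 2 to 4 events, covariate adjustment overfits.
- List the markers, including the number of miRNAs and the time points. State which patients are included (26 or 39), and define the marker-by-outcome family.
- Apply Benjamini-Hochberg across that family at a stated q, for example 10%.
- Report every marker with its effect and confidence interval, and label the results exploratory.
- Do not substitute a multi-marker lasso with bootstrap correction, which is fragile with so few events.

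This costs SAP wording only; no new data, patients or procedures are needed. It limits false markers but does not eliminate them. The price is low power for moderate effects (about 9% at AUC 0.75 and 33% at 0.85 with 4 responders in 26 and 16 markers) and fewer markers declared associated. The SAP should say so.

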### **6.4 Response Assessment/ Duration of Therapy**

Patients will undergo CT scans at week 8 and week 12 (+/- 1 week) following initiation of IL-2 therapy and then after each course (every 10-12 weeks). After the final course (week 36), patients will undergo CT scan evaluation every 12 weeks (+/- 2 weeks) for up to one year or until tumor progression (whichever comes first). If additional scans are performed for clinical reasons, the study schedule may be altered to perform the requisite scans at a more acceptable time point. The change in timing of study scans must be approved by the local PI and documented. For patients who have not shown progression at the end of one year, response will be captured during follow-up for survival (explained below).

Patients with evidence of tumor shrinkage with all lesions measurable and evaluable may receive up to 3 courses of IL-2 therapy. Course 2 will start on or within 2 weeks following day 85 and follow the same schedule as in Course 1. Course 3 can start within 2 weeks of completion of Course 2. Patients not receiving IL-2 during course 2 with tumor shrinkage by week 24 can receive a 2nd course of IL-2 beginning within 2 weeks of week 25.

Patients with no evidence of progression by RECIST 1.1 criteria may receive continued treatment with hydroxychloroquine through one year of initiation of HCQ treatment (Day -14) or until disease progression.

Tumor response will be assessed by the NCI’s Response Evaluation Criteria in Solid Tumors (RECIST) 1.1 guidelines. Patients will undergo tumor evaluation with physical exam and CT scans at week 8 (+/- 1 week) and week 12 (+/- 1 week), then after each course (every 10-12 weeks). After the final course (week 36), patients will undergo CT scan evaluation every 12 weeks (+/- 2 weeks) for up to one year or until tumor progression (whichever occurs first). If additional scans are performed for clinical reasons, the study schedule may be altered to perform the requisite scans at a more acceptable time point. The change in timing of study scans must be approved by the local PI and documented. For patients who have not shown progression at the end of one year, response will be captured during follow-up for survival, which will be done on all patients via telephone contact and medical record review. Patients with progressive disease by RECIST 1.1 criteria will be taken off study.

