## 7.0 LABORATORY STUDIES

The schedule for blood sampling is in Appendix C. Bloods will be sent directly by overnight courier to the UPCI for separation and cryopreservation.

UPCI – IMCPL  
[name]  

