**7.4 Correlate the levels of autophagic markers with measures of clinical outcome in peripheral blood mononuclear cells.** We hypothesize that there will be biomarkers in the peripheral blood that will be specifically associated with induction of autophagy in renal cancer patients. We further hypothesize that these markers will correlate with treatment status, stage, and response to therapy, disease progression and overall survival. To test this hypothesis we will correlate the level of autophagy in the peripheral blood mononuclear cells with these measures of clinical outcome. Blood samples will be collected according to the schedule outlined in Table 6. Peripheral blood mononuclear cells are then separated from whole blood via ficoll hypaque separation and frozen in DMSO. Cells will be lysed for western blot analysis for RAGE, HMGB1, LC3, LC3-2, pre-LC3, caveolin 1, and p62. Levels of autophagic proteins, and RAGE/HMGB1 will then be compared between time points and correlated with tumor clinicopathologic correlates, response to therapy, time to progression, and overall survival.

**7.5. Evaluation of KIR/KIR-ligand Genotype and Response to Therapy.** KIR genotyping will be performed on patient DNA samples by PCR sequence-specific primer technique (SSP Unitray assay, Invitrogen Corporation, Carlsbad, CA) in the UPCI Genomics Facility. KIR-ligand typing

will be performed at low-resolution on the same samples for HLA-B & -C loci by reverse PCR-SSO methodology (LifeMatch assay, Gen-Probe, Inc, Stamford, CT) and for high-resolution HLA-C alleles by direct sequencing (AlleleSEQR assay, Abbott Labs, Des Plaines, IL). The four inhibitory KIR genes (KIR2DL1, KIR2DL2, KIR2DL3, KIR3DL1) evaluated in this study and their corresponding KIR-ligands (HLA-C1, HLA-C2, or HLA-Bw4). KIR/KIR-ligand mismatch will be defined as absence of one or more HLA alleles known to be ligands for the inhibitory KIR genes present, using previously published criteria.

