### **10.8 Progression-free Survival**

Progression-free survival (PFS) is defined as the time from date of first protocol treatment until the date disease progression criteria are met (in responding patients progression criteria uses the reference of the smallest measurements recorded since the treatment started) or date of death from any cause, or is censored at date of last disease assessment for those who have not progressed.

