## Appendix C

### Blood Draw Instructions for Research Labs for Protocol IL-2HQ

#### A Phase II Study of Hydroxychloroquine and Aldesleukin in Patients with Advanced RCC

Comments	Treatment Day	Timepoint	Tube(s) to draw	Storage condition
Hydroxychloroquine is oral	Day -14	Pre-dose of Hydroxychloroquine	2 lge (10ml) Red top 10 lge (10ml) sod. Hep. Green top 1 PAXgene RNA blood tube (2.5ml)	1 on ice or in frig., 1 ambient 10 tubes at ambient temp. on their side 1 tube on ice or in frig
	Course 1 Cycle 1 Day 1 and 2	Please draw blood before pre-treatment ancillary medication is given Pre-dose of IL-2 (post-dose PO HCQ)	2 lge (10ml) Red top 10 lge (10ml) sod. Hep. Green top 1 PAXgene RNA blood tube (2.5ml)	1 on ice or in frig., 1 ambient 10 tubes at ambient temp. on their side 1 tube on ice or in frig
		Just prior to Dose 4 of IL-2 (+/- 1 dose)	1 lge (10ml) Red top	On ice or in frig.
	Course 1 Cycle 1 Day 15 and 16	Pre-dose of Hydroxychloroquine	2 lge (10ml) Green top 1 lge (10ml) Red top	Ambient temp. on their side On ice or in frig.
		just prior to Dose 4 of IL-2 (+/- 1 dose)	1 lge (10ml) Red top	On ice or in frig.
	Course 1 Between Days 60-80	During clinic visit	2 lge (10ml) Red top 10 lge (10ml) sod. Hep. Green top 1 PAXgene RNA blood tube (2.5ml)	1 on ice or in frig., 1 ambient 10 tubes at ambient temp. on their side 1 tube on ice or in frig
	Course 2 Cycle 1 Day 1	Pre-dose of IL-2 (post-dose PO HCQ)	2 lge (10ml) Green top 1 lge (10ml) Red top	Ambient temp. on their side On ice or in frig.
	Course 3 Cycle 1 Day 1	Pre-dose of IL-2 (post-dose PO HCQ)	2 lge (10ml) Green top 1 lge (10ml) Red top	Ambient temp. on their side On ice or in frig.

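### Section 13.2.6 does not fix which blood draw defines a marker change, so late changes can enter PFS and response models after the outcome has already been read

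*Combined protocol and SAP*

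**What the plan says.** Section 13.2.6 states the method: stepwise Cox or logistic regression "to determine if changes of any of the markers in Section 7.4 are related to patient outcomes", after adjustment for the prognostic criteria. It names no landmark, no time-dependent covariate and no rule for a patient whose event comes before a draw. Section 13.2.4 mentions dynamic and post-treatment factors without giving a method for them.

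Section 7.4 is equally open about the covariate: "Levels of autophagic proteins, and RAGE/HMGB1 will then be compared between time points". It refers to Table 6 for the draw times, but Table 6 is the tumor-assessment table. The usable schedule is elsewhere: "The schedule for blood sampling is in Appendix C". Appendix C lists tubes for mononuclear cells at day -14, day 1, day 15, "Course 1 Between Days 60-80", and day 1 of courses 2 and 3 (nominally study days 85 and 169).

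On the outcome side, Section 10.8 has PFS "defined as the time from date of first protocol treatment until the date disease progression criteria are met". Section 10.9 starts survival at the same date, and best overall response in Section 10.3 is also counted from it. Section 5.1 identifies the first day of treatment as day -14. On scans, Section 6.4 says: "Patients will undergo CT scans at week 8 and week 12 (+/- 1 week) following initiation of IL-2 therapy". The same section takes patients with RECIST progression off study.

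**The concern.** A Cox model that starts at day -14 treats its fixed covariates as known at day -14. A change measured at days 60-80 is not known then, and for many patients the PFS event or the first response reading has already happened. There are two possibilities for a patient who progresses at week 8. If a late sample is still taken, the change is measured after the event and may be caused by it. If no sample is taken, the patient drops out of the model because of the outcome, and the result describes only patients who were event-free at the draw. The draws at courses 2 and 3 are more selected still, because further IL-2 courses are confined to patients without progression.

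At stake is the reading of the correlative results. In a trial of about 26 to 39 patients, with stepwise selection over several markers, a marker that merely reacts to progression or response could be reported as related to PFS or response.

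**Working it through.** **The plan's own figure.** The documents give no figure for the 13.2.6 analysis. The nearest is the 12.8-month expected confidence interval width for median survival in Section 13.4. With exponential survival, a 16-month median and 15 months of uniform accrual plus 15 months of follow-up, the event probability is 0.616. That gives 39 × 0.616 = 24.0 events and a width of 2 × 1.96 × 16 / √24.0 = 12.8 months. The figure reproduces, so an exponential model is consistent with the plan's own working.

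**Order of draws and scans.** Week 8 after the start of IL-2 is day 57, with a window of about days 50-64. The late draw opens on day 60, three days after the nominal scan, and the two windows overlap only on days 60-64. The day 1 and day 15 draws come before every scheduled scan.

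**Share of patients with a PFS event before the late draw.**

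Inputs: median PFS 4.3 months (the contemporary high-dose IL-2 trial in Section 2.2) and 3 months (the randomized phase III trial in Section 2.3).

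Formula: 1 − 2^(−t/median). Here t = (day + 14)/30.4375 months if the historical clock is matched to day -14, or (day − 1)/30.4375 months if it is matched to day 1.

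- By day 60, from day -14: t = 74/30.4375 = 2.43 months, giving 32% (median 4.3) to 43% (median 3).
- By day 60, from day 1: t = 59/30.4375 = 1.94 months, giving 27% to 36%.
- By day 80, from day -14: t = 94/30.4375 = 3.09 months, giving 39% to 51%.
- By day 80, from day 1: t = 79/30.4375 = 2.60 months, giving 34% to 45%.

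Across both medians and both clocks this is 27-43% by day 60 and 34-51% by day 80. Section 2.2 itself remarks that in prior studies about half the patients progressed on the first scan.

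**OS.** With a 16-month median, 1 − 2^(−3.09/16) = 0.125. About 12% of patients would have died by day 80.

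**False-positive rate for PFS.** Simulation with n = 26 (the 21 new patients plus the first five at 600 mg/d in Section 2.18) and exponential PFS with median 4.3 months. The draw is 84 days after day -14. The marker is standard normal and unrelated to prognosis, with an assumed 1 SD added when progression came before 71 days (study day 57). The test is a Cox model at nominal 5%. The rate depends on the share of patients with an event before the draw who are still sampled:

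- None sampled: about 6%
- 25%: about 9%
- 50%: about 16%
- All: about 27%
- All, with a 0.5 SD shift: about 11%

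Repeat runs differ by up to about two percentage points. The landmark model gives about 6%.

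**Patients left at a day-80 landmark (from day -14).** 26 × (1 − 0.51) to 26 × (1 − 0.39) is about 13-16. 39 × (1 − 0.51) to 39 × (1 − 0.39) is about 19-24.

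**The case against.** Four points can be made for the plan.

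First, 13.2.6 does not name the days 60-80 draw, and changes to day 1 or day 15 are unaffected. This stands. The defect is that the choice of draw is left open, not that every marker analysis is unsound.

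Second, a reader might infer that the plan as written carries a 27% false-positive rate. The documents do not support that. The figure needs every early progressor to be sampled after the event and an assumed 1 SD shift. Patients with RECIST progression go off study, no research draw is scheduled at the visit about 30 days after discontinuation, and patients whose event is death cannot be sampled later. If no such patients are sampled, the error is about 6%, the same as for a landmark model. What remains then is that the result applies to patients event-free at the draw, which the plan does not say.

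Third, the stated aim is association, and Section 7.4 expects markers to move with progression. This is fair as description. It does not justify using a later measurement as a baseline covariate in a time-to-event model.

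Fourth, response is best overall response, and Section 10.4 requires confirmation at least four weeks later, so a week-8 response is confirmed after the draw. Yet Section 10.5 dates a response from when the criteria are first met. A change measured after that date may be a result of the response.

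A reader might also infer that survival by marker group is inflated by guaranteed survival to sampling. The plan specifies regression, not survival curves by marker group, so this does not describe 13.2.6.

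**Conclusion.** The concern holds for late changes in relation to PFS and response. Roughly a quarter to a half of patients can be expected to have had a PFS event before or during the days 60-80 window, assuming exponential PFS and the protocol's historical medians. The plan has no rule for them. The effect on false positives cannot be fixed from the documents. It runs from negligible to about 27% in the setting simulated, driven by the unknown share of early progressors who are still sampled and by the assumed shift. The simulation covers PFS only. For response, the order of scan and draw is enough to make the point. Early changes are sound and OS is little affected. These are secondary correlative analyses that drive no trial decision, so this is an inexpensive improvement and not a threat to the primary result.

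**What to change.** In 13.2.6:

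- Make the change from day -14 to day 1 or day 15 the main covariate, and name which.
- Analyse changes to days 60-80 and to course 2 or 3 day 1 only by landmark or as time-dependent covariates. A landmark analysis includes patients event-free at the landmark, with follow-up starting there; day 80 would serve for the days 60-80 draw.
- For response, use only changes measured before the first response assessment. The days 60-80 and later draws are then not used to predict response, and the text should say so.
- Point Section 7.4 and Appendix B footnote n to Appendix C instead of Table 6.

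The cost is SAP wording and routine programming, with no new samples or visits. The downside is a smaller late-sample analysis: about 13-16 of 26 patients, or 19-24 of 39, at the day-80 landmark, and no late-draw analysis of response.
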